8.2.3. Safety Analysis

Safety will be analyzed using data collected during the observation period (from the start day of AMEPAROMO treatment to the end day of AMEPAROMO treatment) plus 28 days^d. All adverse events reported in the study will be included in listings.

^c: Because the dosage and administration of AMEPAROMO is “the usual dosage for adults is 1500 mg (potency) of paromomycin sulfate administered orally after meals, divided into 3 doses per day for 10 days”, overdose present was defined as “daily total dose exceeded 1500 mg on at least 1 day, or the duration of treatment is 12 days or more”. Only dose per single dose, number of doses, start day, and end day are collected as records on treatment with AMEPAROMO in the CRF. If AMEPAROMO is taken a total of 30 times in 10 days and the initial dose on the start day (Day 1) is given after lunch or supper, the last dose on the last day (Day 11) will be after breakfast or lunch. Because the duration of treatment from the start day to the end day is calculated to be 11 days in tabulation, the duration of treatment of 12 days or more was selected.

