7.2.6. Observation period

The observation period shall start on the day the treatment with AMEPAROMO begins (Day 1) and end on Day 10 during which patient background information, records on AMEPAROMO treatment, records on concomitant therapies, and records on the treatment status and discontinuation of AMEPAROMO shall be entered in CRFs. When the treatment is discontinued during the observation period, the observation period shall be until the day when AMEPAROMO treatment is discontinued.

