7.3.6. Adverse events

After confirming the occurrence of AEs from the start day of treatment with AMEPAROMO to the end day of the observation period, input the following information. Upon occurrence of any AE, the investigator should take appropriate measures, and promptly report to Pfizer Japan Inc. (hereinafter referred to as the “Sponsor”), and if the causal relationship with AMEPAROMO cannot be ruled out, the investigator should follow up the event until the AE or its sequelae are resolved or stabilized at the level acceptable to the investigator and Sponsor.

In addition, a study should be separately conducted in detail on patients in whom a serious adverse reaction, or an adverse reaction not described in the package insert occurred if it is determined necessary by the Sponsor.

- Presence/absence of AE
- Name of AE
- Date of onset
- Intervention
- Seriousness
- Outcome of the AE to date
- Causal relationship with AMEPAROMO

When an adverse reaction such as diarrhea occurred, and changes in intestinal flora were checked, input the following additional information:

- Result of changes in intestinal flora

If the AE is associated with abnormal change in laboratory values, i.e., clinical laboratory tests, input the following information:

- Laboratory parameter
- Site reference value
- Unit
- Date measured
- Results

Supplement: An AE can be any unfavorable event (including a clinically significant abnormal change in a laboratory value) in a patient occurred after administration of AMEPAROMO whether or not considered related to AMEPAROMO. A serious adverse event (SAE) is an event that results in death, is life-threatening, requires hospitalization or prolongation of existing hospitalization, results in persistent or significant disability/incapacity, is a congenital anomaly/birth defect, or is other medically important events or events possibly resulting in disability.

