9.1. Requirements

The table below summarizes the requirements for recording safety events on the CRF and for reporting safety events on the NIS AE Report Form to Pfizer Safety. These requirements are delineated for three types of events: (1) SAEs; (2) non-serious AEs (as applicable); and (3) scenarios involving drug exposure, including exposure during pregnancy (EDP), exposure during breast feeding, medication error, overdose, misuse, extravasation, and occupational exposure. These events are defined in the section "Definitions of safety events."

| Safety event | Recorded on the CRF | Reported on the NIS AE Report Form to Pfizer Safety within 24 hours of awareness |
|--|--|--|
| SAE | All | All |
| Non-serious AE | All | None |
| Scenarios involving exposure to AMEPAROMO, including EDP, exposure during breast feeding, medication error, overdose, misuse, extravasation; lack of efficacy; and occupational exposure | All (regardless of whether associated with an AE), except occupational exposure | All (regardless of whether associated with an AE) |

For each AE, the investigator must pursue and obtain information adequate both to determine the outcome of the AE and to assess whether it meets the criteria for classification as an SAE (see section “Serious adverse events” below).

Safety events listed in the table above must be reported to Pfizer within 24 hours of awareness of the event by the investigator **regardless of whether the event is determined by the investigator to be related to AMEPAROMO**. In particular, if the SAE is fatal or life-threatening, notification to Pfizer must be made immediately, irrespective of the extent of available event information. This timeframe also applies to additional new (follow-up) information on previously forwarded safety event reports. In the rare situation that the investigator does not become immediately aware of the occurrence of a safety event, the investigator must report the event within 24 hours after learning of it and document the time of his/her first awareness of the events.

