9.2. Reporting period

For each patient, the safety event reporting period begins at the time of the patient’s first dose of AMEPAROMO, and lasts through the end of the observation period of the study, which must include at least 28 calendar days following the last administration of AMEPAROMO; a report must be submitted to Pfizer Safety (or its designated representative) for any of the types of safety events listed in the table above occurring during this period. If a patient was administered AMEPAROMO on the last day of the observation period, then the reporting period should be extended for 28 calendar days following the end of observation.

If the investigator becomes aware of an SAE occurring at any time after completion of the study and he/she considers the SAE to be related to AMEPAROMO, the SAE also must be reported to Pfizer Safety.

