2.1. Study Design

This investigation is a multicenter open study in patients who received AMEPAROMO for treatment of intestinal amebiasis. Patients who have never been treated with AMEPAROMO will be enrolled using a central registration system. The observation period shall start on the day the treatment with AMEPAROMO begins (Day 1) and end on Day 10. The main effectiveness analysis item will be the proportion of cyst negative based on the results of examination of cysts up to 3 months after the completion of observation period (or discontinuation of treatment), and clinical response assessed by the investigator will also be evaluated. A target sample size of 100 patients was selected. The rationale for the target sample size is shown below.

- *Rationale*

The number of patients who will receive AMEPAROMO may be extremely small, but 100 patients were chosen as a sample size that can be collected during a certain period of time from the viewpoint of the feasibility of the study.

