8.2.3.1. Adverse Drug Reactions

- **All adverse drug reactions**

The number and proportion of patients with adverse drug reactions will be tabulated by SOC and PT.

- **Serious adverse drug reactions**

The number and proportion of patients with serious adverse drug reactions will be tabulated by SOC and PT.

- **Details of adverse drug reactions**

The number and proportion of patients with adverse drug reactions will be tabulated by SOC and PT for each of the following items.

- Seriousness [serious, non-serious]
- Expected/unexpected [expected, unexpected]
- Intervention [discontinuation, temporarily discontinued or dose reduced]
- Outcome [not recovered, recovered with sequela, recovering, resolved/recovered, unknown]

In addition, the number and proportion of patients with adverse drug reaction that meets all of the following items will be tabulated by SOC and PT:

- The seriousness was considered “non-serious”;
- The intervention was “discontinuation”, “temporary discontinued”, or “dose reduced”
- The outcome was “not recovered” or “recovered with sequela”.

If the same adverse drug reaction (the same PT) occurs more than once in the same patient, it will be handled as follows in the tabulation of the number of patients with events:

- Seriousness: If both serious and non-serious events are reported, “serious” will be adopted.
- Expected/unexpected: If both expected and unexpected events are reported, “unexpected” will be adopted.
- Number of days to onset: The number of days to the first event will be adopted.
- Intervention: If multiple types of action are reported, one of discontinuation, temporarily discontinued or dose reduced, or other (none, dose increased), in descending order of precedence, will be adopted.

^d: The collection period was specified as the observation period plus 28 days because the period of reporting of safety information collected using the NIS AE Report Form of the study is up to 28 days after the end day of treatment.

- Outcome: The outcome of the last occurring event will be used.

- **Time to adverse drug reaction**

The number of patients who experienced an adverse drug reaction will be tabulated by time to first development (<3 days, ≥ 3 to <7 days, ≥ 7 to <10 days, ≥ 10 days), by SOC and PT.

- **Details of serious adverse drug reactions**

The number and proportion of patients with serious adverse drug reactions will be tabulated by expected/unexpected status by SOC and PT.

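### The SAP justifies its treatment-plus-28-days ADR window by a form that does not take non-serious AEs, and the protocol contradicts itself on whether the CRF covers those 28 days.

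*SAP*

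**What the plan says.** SAP 8.2.3 sets the safety analysis period as the "observation period (from the start day of AMEPAROMO treatment to the end day of AMEPAROMO treatment) plus 28 days". Footnote d gives a single reason for the 28 days: "the period of reporting of safety information collected using the NIS AE Report Form of the study is up to 28 days after" the end of treatment.

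The table in Protocol 9.1 has one column for the CRF and one for reporting on that form within 24 hours. Its row for non-serious events reads "Non-serious AE | All | None".

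Protocol 7.3.6 sets the CRF task for AEs: "After confirming the occurrence of AEs from the start day of treatment with AMEPAROMO to the end day of the observation period", the details are entered. The next sentence adds: "Upon occurrence of any AE, the investigator should take appropriate measures, and promptly report to Pfizer Japan Inc".

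The length of the observation period is given in several places:
- SAP 2.1, in line with Protocol 7.2.6: "The observation period shall start on the day the treatment with AMEPAROMO begins (Day 1) and end on Day 10".
- Protocol 7.2.6, for early stopping: "the observation period shall be until the day when AMEPAROMO treatment is discontinued".
- Protocol 9.2, on the same observation period: "which must include at least 28 calendar days following the last administration of AMEPAROMO".
- SAP 8.2.3: first to last day of treatment, as quoted above.

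**The concern.** The incidence of adverse reactions, serious and non-serious together, is a main safety item (Protocol 7.7). It feeds the periodic safety update reports and the reexamination application (SAP 3). A proportion over treatment plus 28 days can be read at face value only if events of both kinds were sought over that whole time.

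The reason given in footnote d works for serious events, which all go on the form. It does not work for non-serious events, for which the form is not the routine route. If CRF confirmation also stops on Day 10 or at discontinuation, serious ADRs are sought for about 38 days and non-serious ADRs for about 10. The overall incidence could then be too low and the split by seriousness hard to interpret. A listing of reported events cannot show whether an absence of late non-serious ADRs means that none occurred or that none were asked for.

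**Working it through.** **Passages side by side**

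1. The form: Protocol 9.1 requires all SAEs on it and no non-serious AEs. Footnote d therefore supports the 28 days for serious ADRs only.
2. The CRF: 9.1 requires all non-serious AEs on it, but the table gives no end date. The end date comes from 7.3.6, which points to the end of the observation period.
3. The observation period: an end on Day 10 cannot include 28 days after a last dose on Day 10, so 7.2.6 and SAP 2.1 conflict with 9.2.
4. The SAP's own reading: 8.2.3 adds 28 days to the observation period, so it places those days outside it. That is the short reading. It agrees with 7.2.6 for a 10-day course or one stopped early, but not for other lengths.

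**Days in the SAP window without scheduled CRF confirmation of non-serious AEs**

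Inputs: window end = last dose day + 28 (SAP 8.2.3). CRF end under 7.2.6 = Day 10, or the day of discontinuation if earlier. The Day-11 case is the 30-dose course begun after lunch or supper in SAP footnote c. The Day-5 and Day-8 cases are examples.

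| Course | Window ends | CRF ends (7.2.6) | Unscheduled days |
|---|---|---|---|
| Stopped early on Day 5 | 5 + 28 = 33 | 5 | 33 − 5 = 28 |
| Last dose Day 8, counted as complete | 8 + 28 = 36 | 10 | 36 − 10 = 26 |
| Last dose Day 10 | 10 + 28 = 38 | 10 | 38 − 10 = 28 |
| Last dose Day 11 | 11 + 28 = 39 | 10 | 39 − 10 = 29 |

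Under 9.2 the observation period reaches at least last dose day + 28, so the unscheduled part is 0 in every row. These are days, not a measure of bias.

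**Effect on the incidence**

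The documents give no ADR rate and no late-onset rate, so there is no planned figure to reproduce and no under-count to compute. For scale only, assume that 10 of the planned 100 patients have a recorded ADR and that k more have a late, unreported non-serious ADR as their only ADR. Exact 95% intervals, the SAP 8.1.3 method:

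- k = 0: 10/100 = 10.0% (4.9 to 17.6)
- k = 1: 11/100 = 11.0% (5.6 to 18.8)
- k = 3: 13/100 = 13.0% (7.1 to 21.2)

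Each such patient moves the incidence by one percentage point. Both the 10 and the k are assumptions.

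**The case against.** The strongest reply is that the protocol, read as a whole, intends full collection, and much of this stands:

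- The CRF cell for non-serious AEs says *All*, with no time limit.
- Protocol 9.2 applies to every event type in the 9.1 table, which includes non-serious AEs. Its closing sentence on the reporting period adds 28 days for a patient dosed on the last day of observation, which is the standard 10-day course.
- Protocol 7.3.6 asks for prompt reporting of any AE, and 7.2.6 does not name AEs among the records it confines to Day 1 to Day 10.
- Section 9 treats the form as part of the CRF. Section 9.3 sends events of unknown causality for 24-hour reporting, and the exposure and lack-of-efficacy scenarios in 9.1 bring in others.

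None of these sets a CRF end day for non-serious AEs. The closing sentence of 9.2 extends the reporting period, not the observation period that 7.3.6 uses. Prompt reporting of a noticed event is not the same as scheduled confirmation. Table 1 does not help, because the end of its AE arrow cannot be read in the extracted text.

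The reply is also right on output. SAP 8.2.3.1 already tabulates ADRs by time to first onset, with a last category of 10 days or more, and all reported AEs are listed. Late events that were reported will therefore be largely visible. That table is not split by seriousness and does not follow the end of observation in patients who stop early.

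Finally, the analyses are exploratory with no decision rule (SAP 4.1, 4.2). SAP 8.2.3.5 starts a factor analysis for ADRs above 10%, and a step from 10 to 11 patients with the same term would cross that line. Such an example is built to sit on the threshold and carries little weight.

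**Conclusion.** The point holds as a contradiction in the documents, not as a demonstrated loss of data. Footnote d cannot support the window for non-serious ADRs, and 7.2.6 with SAP 2.1 cannot be squared with 9.2 on the length of the observation period.

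A reader might infer that late non-serious ADRs are not collected and that the incidence is biased downward. The documents do not support that: several provisions point to full collection, and actual site practice is not described. Nor do they support the inference that 28 days is the gap for every course ending by Day 10, since a short course counted as complete leaves fewer. A reader might also conclude that the 28-day window is the wrong choice, but it matches the duration in 9.2.

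Size: 26 to 29 unscheduled days for the courses worked through if 7.2.6 governs, 0 if 9.2 governs. The under-count is unknown and may be 0. The harm is in what the reported incidence means. It deserves correction because the incidence is a main item and the repair is cheap; confidence is medium, because whether a gap exists turns on which provision sites followed.

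**What to change.** 1. Reconcile Protocol 7.2.6, 7.3.6, 9.1 and 9.2 with SAP 2.1 and 8.2.3, so that there is one observation period and one stated day to which non-serious AEs are recorded on the CRF.
2. Correct footnote d so that the window for non-serious ADRs does not rest on the NIS AE Report Form.
3. Keep the treatment-plus-28-days incidence as the main figure.
4. Extend the time-to-onset table in SAP 8.2.3.1 by seriousness and by onset within versus after the CRF observation period. A wholly new table is not needed.
5. Only if collection to 28 days cannot be confirmed, footnote the incidence to say that non-serious events after the CRF observation period were not systematically collected.

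Cost: wording changes and slightly more table work. Onset date and seriousness are already collected (Protocol 7.3.6), and the SAP change log shows that a within/outside tabulation was once planned. The downside is a possibly less favourable footnote; the incidence itself does not change.

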8.2.3.1. Adverse Drug Reactions

- **All adverse drug reactions**

The number and proportion of patients with adverse drug reactions will be tabulated by SOC and PT.

- **Serious adverse drug reactions**

The number and proportion of patients with serious adverse drug reactions will be tabulated by SOC and PT.

- **Details of adverse drug reactions**

The number and proportion of patients with adverse drug reactions will be tabulated by SOC and PT for each of the following items.

- Seriousness [serious, non-serious]
- Expected/unexpected [expected, unexpected]
- Intervention [discontinuation, temporarily discontinued or dose reduced]
- Outcome [not recovered, recovered with sequela, recovering, resolved/recovered, unknown]

In addition, the number and proportion of patients with adverse drug reaction that meets all of the following items will be tabulated by SOC and PT:

- The seriousness was considered “non-serious”;
- The intervention was “discontinuation”, “temporary discontinued”, or “dose reduced”
- The outcome was “not recovered” or “recovered with sequela”.

If the same adverse drug reaction (the same PT) occurs more than once in the same patient, it will be handled as follows in the tabulation of the number of patients with events:

- Seriousness: If both serious and non-serious events are reported, “serious” will be adopted.
- Expected/unexpected: If both expected and unexpected events are reported, “unexpected” will be adopted.
- Number of days to onset: The number of days to the first event will be adopted.
- Intervention: If multiple types of action are reported, one of discontinuation, temporarily discontinued or dose reduced, or other (none, dose increased), in descending order of precedence, will be adopted.

^d: The collection period was specified as the observation period plus 28 days because the period of reporting of safety information collected using the NIS AE Report Form of the study is up to 28 days after the end day of treatment.

- Outcome: The outcome of the last occurring event will be used.

- **Time to adverse drug reaction**

The number of patients who experienced an adverse drug reaction will be tabulated by time to first development (<3 days, ≥ 3 to <7 days, ≥ 7 to <10 days, ≥ 10 days), by SOC and PT.

- **Details of serious adverse drug reactions**

The number and proportion of patients with serious adverse drug reactions will be tabulated by expected/unexpected status by SOC and PT.

- **Adverse drug reactions by patients of included/excluded in the safety analysis set**

In CRF-collected patients, the listing of adverse drug reactions in patients excluded from the safety analysis set will be prepared. In addition, the number of patients with events will be tabulated by SOC and PT.

- **Status of development of adverse drug reactions in contraindicated patients**

The listing of contraindicated patients including the status of development of adverse drug reactions will be prepared. The number and proportion of patients with adverse drug reactions will be tabulated by patients who do or do not meet contraindications by SOC and PT as necessary.

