7. HANDLING OF MISSING DATA

When the causal relationship of adverse events is missing, the data will be handled as “related” for counting. When the seriousness/outcome of adverse events and action taken with

AMEPAROMO for the adverse events are missing, the data will be handled as “unknown” for counting.

For effectiveness endpoints, missing data will not be imputed.

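### The SAP's ADR detail tables have no cell for a fatal outcome or for unknown seriousness, and for a repeated reaction they keep the last outcome rather than the worst

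*SAP*

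**What the plan says.** SAP 8.2.3.1 plans tables of patients with ADRs, by SOC and PT, for several characteristics. Two matter here:

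- Outcome: "Outcome [not recovered, recovered with sequela, recovering, resolved/recovered, unknown".
- Seriousness: "Seriousness [serious, non-serious".

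SAP 7 sets the missing-data rule: "When the seriousness/outcome of adverse events and action taken with" the drug "for the adverse events are missing, the data will be handled as “unknown” for counting". SAP 8.2.3.2 tabulates serious and non-serious adverse events, with no third group.

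When the same PT occurs more than once in a patient, SAP 8.2.3.1 reduces the episodes to one record:

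- Seriousness: "If both serious and non-serious events are reported, “serious” will be adopted".
- Expectedness: "If both expected and unexpected events are reported, “unexpected” will be adopted".
- Intervention: discontinuation first, then suspension or dose reduction, then other, "in descending order of precedence, will be adopted".
- Outcome: "Outcome: The outcome of the last occurring event will be used".

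The same section adds a table of patients whose ADR was non-serious, led to an intervention and had a poor outcome (not recovered, or sequela).

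**The concern.** The outcome list leaves out a result that the protocol foresees. Death is the first seriousness criterion in Protocol 7.3.6 and 9.4.2, and Protocol 9.1 requires immediate notification of fatal events. No other table described in SAP 8 counts deaths.

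The seriousness split does not fit the SAP's own missing-data rule, which creates a value with no row to go in. Outcome, by contrast, does have an 'unknown' category.

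The repeat rule treats outcome differently from the other three graded items and gives no reason. A sequela recorded for one episode disappears from the outcome table if a later episode of the same PT resolves.

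At stake is whether the detail tables are complete and whether they look more favourable than the data behind them.

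**Working it through.** The documents give no figure on this point, so there is nothing to reproduce. The check sets the rules against the values they must hold.

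**1. Outcome.** Protocol 7.3.6 collects the outcome of each event on the CRF. The possible results include death; the SAP has five categories and none is fatal. The SAP does not say where a recorded death goes. The CRF's own outcome options are not shown in the documents.

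**2. Seriousness.** SAP 7 implies three values: serious, non-serious and unknown. SAP 8.2.3.1 and 8.2.3.2 name two. If any event has missing seriousness, the two rows do not account for all events. Incomplete records are plausible. Protocol 7.9 warns of missing chart information, and SAP 7 counts events with missing causality as related, which brings incompletely reported events into the ADR tables. The two gaps can combine. SAP 6.1 makes an event serious only if the investigator judged it so, so a fatal ADR with seriousness left blank would appear as neither serious nor fatal in the detail tables.

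**3. Repeat rule.**

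| Item | Value kept for a repeated PT |
|---|---|
| Seriousness | worst ('unknown' not ranked) |
| Expectedness | unexpected over expected |
| Intervention | strongest action |
| Outcome | last |

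Take two episodes of one PT and the SAP's five outcome categories.

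- Ordered pairs: 5 × 5 = 25.
- Pairs in which the first outcome is poor ('not recovered' or 'recovered with sequela', 2 options) and the last is 'recovering', 'resolved/recovered' or 'unknown' (3 options): 2 × 3 = 6. The last-event rule drops the poor outcome in these 6 of 25, of which 3 start with a sequela.
- Under a worst-known-outcome rule, 0 of 25 drop it.
- With the four known outcomes only: 4 × 4 = 16 ordered pairs. The last is milder than the worst in 4 × 3 / 2 = 6, whichever of the two poor outcomes is ranked worse.

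These are counts of possible patterns. The documents give no rates from which to turn them into probabilities.

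**4. Three-condition table.** Suppose episode 1 led to suspension and resolved, while episode 2 needed no action and did not recover; both were non-serious. Collapsed, the record reads non-serious, suspended, not recovered. It qualifies although neither episode does. Conversely, an episode with suspension and a sequela drops out if a later episode resolves. Either happens only if the table is built from collapsed records, which the SAP neither states nor rules out.

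**5. Weight of one case.** At the target of 100 patients (Protocol 7.5.1), one patient is 1/100 = 1.0% of the table denominator, and slightly more if the exclusions in SAP 5.1 reduce the safety set.

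**The case against.** The strongest reply is that little is actually lost, and most of it stands.

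- **Main safety result.** A reader might infer that the main safety output changes. It does not. Protocol 7.7 names the occurrence of main adverse reactions and the incidence of adverse reactions as the main items. The all-ADR table serves these and uses neither outcome nor seriousness.
- **Lost cases.** SAP 8.2.3 lists all adverse events, and SAP 9 plans in-text listings of ADRs and of serious ADRs. An ADR of unknown seriousness stays in the overall ADR and adverse event tables. A fatal ADR marked serious also appears in the serious ADR tables.
- **Overwritten or misfiled deaths.** A reader might infer that the last-event rule can erase a death. Death ends the sequence, so that rule would keep it. Nor does any SAP rule send a death to 'not recovered' or 'unknown'; SAP 7 reserves 'unknown' for missing values. The accurate statement is that death has no named cell.
- **Change of conclusion.** A reader might argue that one misfiled case turns a positive finding into none observed, and cite the exact upper limit for zero events in 100. That limit describes any zero count and does not measure this defect, and the case would still be listed.
- **Closed lists.** The intervention bracket omits the 'other' level that the repeat rule uses, so the brackets may be abbreviated. That is possible, but the SAP then leaves the missing cells unstated.
- **Last status.** Protocol 7.3.6 collects outcome to date, so the last value is defensible for 'not recovered'. It is not for a sequela, which a later recovered episode does not undo.
- **Three-condition table.** Its wording, in the singular, can be read as one event meeting all three conditions.

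Missing seriousness should also be uncommon: Protocol 9.1 requires enough information to assess it, and Protocol 7.6.3.2 allows queries.

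**Conclusion.** The point holds in a limited form. As written, a fatal ADR has no outcome cell; an event of unknown seriousness has no row in SAP 8.2.3.1 or 8.2.3.2; and an earlier sequela is replaced when a later episode of the same PT recovers. The secondary detail tables can therefore be incomplete or too favourable. Overall ADR incidence and the listings are unaffected.

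Few patients are likely to be involved. The overwriting needs the same PT at least twice in one patient within the safety analysis window of treatment plus 28 days, with the poor outcome first. The documents give no frequency for this. The conclusion assumes that the bracketed categories are the ones to be programmed and that the repeat rule is applied as stated. It is worth correcting because listings do not repair a summary table and the correction is cheap.

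**What to change.** In SAP 8.2.3.1 and 8.2.3.2:

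1. Add 'fatal' to the outcome categories.
2. Add an 'unknown' seriousness row to the ADR detail table and to the serious/non-serious adverse event tables, and state how 'unknown' ranks against serious and non-serious when a PT repeats.
3. For a repeated PT, tabulate the worst known outcome. At a minimum, keep fatal first and then sequela over a later recovery. Use 'unknown' only if no episode has a known outcome, so that a missing value never displaces a known one. Alternatively, show both the worst and the last outcome.
4. State that the three-condition table is evaluated on single events, not on collapsed records.

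The cost is SAP wording and table shells, with no change to the protocol's main safety items. The only downside is that outcome tables may look slightly less favourable.
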